B.4 Preliminary studies. In addition to studies establishing our enrollment and assessment procedures,^{18, 49} we have conducted preliminary studies to demonstrate the feasibility of intervention procedures and acceptance by nursing home staff.²⁰ *First, we developed standardized procedures and training (Appendix 2) in collaboration with a HELP Center of Excellence. At start up and thereafter we instituted a weekly whole-team rounds and discussion of each patient to optimize intervention fidelity.* In 2013 we implemented the intervention during 149 acute illness episodes at the study site, for a rate of 14 per month. 63% of patients were female, 37% Spanish-speaking, with average age of 83 years. The mean Brief Interview of Mental Status score was 7.5 (max possible score 15), indicating moderate cognitive impairment. The most common illnesses initiating receipt of the intervention were infections of bladder (29%), lower respiratory tract (18%), and skin (10%). Intervention CNAs delivered on average 14.2 visits over a 13.5 day span per episode, with average visit length of 30.5 minutes. Patient adherence to each of the components per visit ranged from 70-94% (Table 1), with a goal of 75%. The most common reasons for not receiving a component were patient refusal and patient off floor or unavailable. In a semi-structured interview of 28 patients who were capable of providing feedback, 27 had high satisfaction with the intervention and endorsed the value of each intervention component. *On days when 2 CNAs visited the same patient (n=179), percent agreement on provision of the key intervention components (orientation, mobility, fluids) was high, ranging from 80-93%, indicating excellent fidelity.* Among 4 physicians and 13 unit nursing staff who participated in a semi-structured interview, all indicated that communication between unit and intervention staff was effective and 14 endorsed that work stress was lower with the intervention, indicating good integration between intervention and unit nursing activities. *Staff*

indicated that they appreciated and recognized the intervention CNA as a mobile staff member who delivered focused services to patients on the floors, but not daily care. Delirium occurred during 22% of acute illnesses and 5% of patients were transferred to the hospital during or within 30 days after finishing the intervention.²⁰

B.5 Investigative team

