The PI has conducted innovative research to improve care in nursing homes, including interventions with CNAs, that has been widely cited and adopted.^{28, 59-60} He has worked with nursing homes in New York and nationally to implement innovative models of care. [name] (co-investigator) is the developer of HELP and the Confusion Assessment Method measure, and brings practical clinical trial experience.^{19, 57} [name] (Data Coordinating Center lead) has extensive experience in nursing home based research, measurement, and oversight of analyses from clinical studies.⁶¹ Advisory group members have been selected who provide expertise in the areas of delirium ([name]), nursing home ([name]), and long-term care nursing ([name]).

C. APPROACH

C.1 Overview. We propose to perform a controlled trial of a multicomponent intervention to prevent delirium at a large nursing home in New York City. The trial will be randomized by unit and evaluator-blinded. We will randomly assign 17 long-term care units to intervention or control and screen nursing home patients on each unit who experience onset of an acute change in condition according to established criteria and enroll 306. Those assigned to intervention (n=153) will receive daily visits from a mobile CNA trained to provide services to counter established risks for delirium, including dehydration, immobility, cognitive impairment, undernutrition, and sleep problems, for the duration of the acute illness and for 1 week following, in collaboration with the patient's primary medical and nursing team. Patients assigned to control (n=153) will receive usual care from the unit-based team. Delirium will be assessed 5 days a week by a research assistant (RA) blinded to study hypotheses and group assignment. Cognitive and physical function decline and hospital transfer will be ascertained during a 1 month follow-up period. We will conduct analyses to compare outcomes between intervention and control, as well as examine associations between outcomes and intervention features such as number and duration of visits. We will use regression models to adjust for covariates and effects of clustering.

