
C.3 Assignment by unit. This is a cluster randomized trial; units will be assigned to intervention or usual care arms. This design will prevent a unit from having patients in both groups and the likelihood of contamination.

Prior to initiating study enrollment, a biostatistician from the Data Coordinating Center (DCC, at a separate location) will assign units to intervention or usual care using a SAS macro. Units are uniform (e.g., there are no specialized dementia units) except that 1) 1 unit has equipment and programs for visually impaired, and 2) some units are larger (38-42 beds) than others (34-35 beds). Thus, the randomization procedure will maintain approximate balance by randomly assigning 5 larger and 3 smaller units to one arm and 4 larger and 5 smaller units to the other. Each unit will keep its assignment for the duration of the study. With rolling enrollment and a planned sample size of 306 we anticipate enrolling approximately 18 patients per unit (mean cluster size = 18).

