Dehydration	Hydration protocol: two 6-ounce cups of fluid by mouth daily	All patients except if not indicated as per nursing or medical team; e.g., those with congestive heart or renal failure with or at risk for fluid overload	1) Dehydration is delirium risk factor ^{64, 66} 2) Hi pulse & low BP assoc w/delirium ⁶⁵ 3) Rehydration may be effective ^{19, 34}	86% (178 refusals; 80 off floor or unavailable; 25 medical contraindicat)
Undernutrition	1) Provision of snack 2) Meal assistance	All patients receive snack unless 15 min before or after a meal	Undernutrition associated with delirium ⁶⁷	70% (385 refusals; 81 off floor or unavailable)
Sleep/relaxation	Sleep and relaxation protocol: massage, warm drink, quiet music	Patients who report sleep difficulties to intervention team	Avoiding sedative effective ¹⁹	80% (34 off floor /unavail; 12 time limit)
Medications	Medication alerts to medical team of meds associated w/delirium	All patients.	1) AGS criteria meds assoc w/ delirium ⁶³ 2) Med review effective ³⁵	--

*Per visit adherence data during 2434 visits, with top reasons patient did not receive a component.

C.5 Outcomes and variables. For intervention and control patients, a trained RA will use the Confusion Assessment Method (CAM), a widely-used, validated measure,⁵⁷ to ascertain incident delirium each weekday during treatment of the acute illness and for 7 days afterward. Delirium severity will be ascertained using the Delirium Index (DI), which has been shown to be reliable in patients with and without underlying dementia and its validity tested in a nursing home population.^{6, 58} Cognitive and physical function will be ascertained using the nursing home Minimum Data Set (MDS) Cognitive Performance⁶⁸ and Activities of Daily Living⁶⁹ scales, and the Brief Interview of Mental Status⁷⁰ at illness onset and 1 month after illness onset. These scales have been tested in the nursing home population and they are performed quarterly in all Medicare-certified facilities, making it possible to collect values on these measures from the medical record and establishing a pre-acute

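### Unit assignment is balanced on size alone, although unit-level cognition and function could be balanced cheaply before assignment and no covariate is pre-specified

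*Combined protocol and SAP*

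**What the plan says.** C.1 states the design: "We will randomly assign 17 long-term care units to intervention or control". C.3 has a statistician at the Data Coordinating Center (DCC) make the assignment with a SAS macro before enrolment starts, and each unit then keeps its arm throughout.

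The reason for balancing on little is given in C.3: "Units are uniform (e.g., there are no specialized dementia units". Two exceptions are named. One is that "1 unit has equipment and programs for visually impaired"; the other is that "some units are larger (38-42 beds) than others (34-35 beds". Only size enters the allocation rule, by "randomly assigning 5 larger and 3 smaller units to one arm and 4 larger and 5 smaller units to the other". The section does not say which arm receives 8 units and which 9, or how the unit for visually impaired residents is handled.

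Other sections bear on the choice:

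- Table 1 lists cognitive impairment as a risk factor for delirium, and the delirium risk score in Table 2 includes it.
- C.5 says of the MDS cognitive and ADL scales and the Brief Interview of Mental Status that "they are performed quarterly in all Medicare-certified facilities, making it possible to collect values on these measures from the medical record".
- C.1 promises regression adjustment for covariates, but C.7 leaves the need for them to be settled after possible sources of bias have been examined. It names none.
- B.4 reports that "In 2013 we implemented the intervention during 149 acute illness episodes at the study site". It does not say which units took part.

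**The concern.** The number of randomised items is 17, not 306. With so few, simple chance can leave one arm with units whose residents are, on average, more cognitively impaired or more dependent. Enrolling more patients per unit does not correct this. The absence of dementia units does not show that mean cognition or function is equal across 17 units.

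The plan has two places to deal with this and uses neither firmly. At the design stage the relevant scores are obtainable but not used. At the analysis stage the covariates are to be chosen after the data have been inspected. If a visible imbalance arises, readers will question the comparison, and any adjustment will look chosen after the fact. What is at stake is precision and credibility.

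**Working it through.** **Inputs.** 17 units, 306 patients and the size scheme (C.1, C.3); ICC .01, cluster size 18, delirium 35% versus 18% (C.6). Bed midpoints of 40 and 34.5 are my assumption within the stated ranges.

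**1. The plan's own figures.** 306 / 17 = 18.0 per unit. VIF = 1 + (18 − 1) × .01 = 1.17. Units: (5 + 3) + (4 + 5) = 17, so 9 larger and 8 smaller. All reproduce.

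**2. Chance imbalance under the stated scheme.** For a unit-level covariate in between-unit SDs, the SD of the arm difference is √(1/8 + 1/9) = 0.486. The normal approximation gives P(|difference| > 0.5) = 2 × [1 − Φ(0.5 / 0.486)] = 0.30. Simulation with 17 standardised units gives 0.32, and 0.13 for a difference above 0.75. These figures follow from having 8 versus 9 units; they use no cognition data from this site.

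**3. What constraint would achieve.** The stated scheme has C(9,5) × C(8,3) = 126 × 56 = 7,056 allocations. I scored each on two simulated unit-level covariates and kept the best-balanced 10% (about 705). The root-mean-square imbalance falls from 0.49 to about 0.12 unit-SD, and differences above 0.5 SD disappear. As a separate feasibility check, requiring both covariates to lie within 0.25 SD leaves about 1,000 allocations (614 to 1,233 over 100 simulated covariate sets), so plenty of randomness remains.

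**4. Size on the outcome scale.** At 35% delirium and ICC .01:

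- between-unit SD = √(.01 × .35 × .65) = 0.0477, or 4.8 points;
- SD of the arm difference due to units = 0.0477 × 0.486 = 0.0232, or 2.3 points;
- target difference = 35 − 18 = 17 points.

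At an assumed ICC of .03 to .05 the 2.3 points become 4.0 to 5.2.

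**5. Ceiling on the gain.** Removing all between-unit variation would take the VIF from 1.17 to 1. The standard error would fall by 1 − 1/√1.17 = 7.5%, about 8%. Balancing two scores removes only the part of that variation which they explain.

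**6. Scale of the covariate imbalance.** If the covariate also had an ICC of .01 (assumed), one between-unit SD would be √.01 = 0.10 patient-SD, so 0.5 unit-SD would be about 0.05 patient-SD.

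**7. The size split.** Under the plan, beds are 5 × 40 + 3 × 34.5 = 303.5 against 4 × 40 + 5 × 34.5 = 332.5, a gap of 29. Splitting the smaller units 4:4 gives 4 × 40 + 4 × 34.5 = 298 against 5 × 40 + 4 × 34.5 = 338, a gap of 40. Over the stated bed ranges the gaps are 26–32 and 38–42.

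**The case against.** The sponsor can fairly say that randomisation gives no expected bias, that between-unit variation is already in the VIF and in the modelled clustering, and that cognition, function and a delirium risk score are collected on every patient and can be adjusted for. Patient-level adjustment also addresses the people actually enrolled, whereas unit means include hospice and nonverbal residents who cannot enter. All of this stands, and it limits the point to a modest gain. It does not answer the lack of pre-specified covariates, and it is no reason to leave free information unused at assignment.

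Three stronger readings are tempting and should be resisted:

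- **That the 3:5 split of smaller units is a mistake because 4:4 was available.** A 4:4 split brings the share of larger units closer (50.0% versus 55.6%, against 62.5% versus 44.4%), but the plan's split is closer on total beds. Nothing in the documents ties unit size to delirium. This is a trade-off, not an error.
- **That the 2013 pilot left some units already exposed, so that control units would dilute the effect.** No section says exposure differed by unit; spread evenly, 149 / 17 is about 9 episodes each. B.2 has a dedicated mobile nursing assistant deliver the intervention, not unit staff, and without teaching or advising them. Carry-over in unit practice is therefore speculative.
- **That a harmful imbalance is likely.** The 32% is in between-unit SDs, which are small at the plan's ICC.

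**Conclusion.** The point holds as a cheap improvement. C.3 balances on size alone, the assertion that units are alike is not supported for cognition or function, suitable scores are on file before assignment, and no covariate is fixed in advance. About one allocation in three would leave a given unit-level covariate more than 0.5 between-unit SD apart, and constrained selection within the plan's own scheme virtually removes that.

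The consequence is modest: an SD of about 2.3 points against a 17-point target, and at most about an 8% reduction in standard error. This rests on the plan's ICC of .01; a larger ICC would raise the value of balancing. The 0.12 figure comes from simulated covariates, so the result with the site's own scores will differ somewhat. The documents do not support a claim of bias, of a wrong size split, or of contamination from the pilot.

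**What to change.** In C.3, keep the stated size scheme and add a constraint:

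1. Before assignment, extract each unit's mean MDS Cognitive Performance and ADL scores from the latest quarterly assessments.
2. Have the DCC macro list the 7,056 allocations and score each on the between-arm difference in the two means.
3. Draw one at random from the best-balanced 10%, then choose by coin toss which side is intervention.
4. Use 2013 pilot episodes per bed as a third criterion only if site records show that they varied across units.

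In C.7, pre-specify the patient-level versions of the two scores as covariates in the GLIMMIX model; the pre-illness values in Table 2 would serve. A sentence in C.3 should also acknowledge that the unit for visually impaired residents can fall in only one arm, since reduced vision is part of the delirium risk score.

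The cost is one extract from existing records, a macro change and two covariates carried into the analysis. The constraint must be in place before assignment, because units do not change arm afterwards.

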C.6 Power and effect size. Based on our previous studies and the known impact of HELP on delirium,¹⁹ we hypothesize observing a clinically meaningful 40-60% relative reduction in new delirium from 35% to between 15% and 20%. Power calculations have been performed treating delirium as a binary (CAM) and continuous (DI) outcome and accounting for clustering of observations by unit and for correlations over time. For the binary variable, new delirium is defined as when delirium occurs any time during the illness period. Sample size was calculated (Figure 1) with the continuity correction,⁷²⁻⁷³ with assumed reliability (R)=.72; groups (g)=2; cluster size (by unit)=18; intraclass correlation (ICC)=.01; and variance inflation factor (VIF)=1+(cluster size-1)*ICC=1.17. With $\alpha=.05$ and ρ (estimated average correlation of the outcome measures over time)=0.60, a sample size of 150 per group will provide 80% power to detect a group difference in new delirium from 35% (baseline)

$$\text{Figure 1. } n' = \frac{(z_{\alpha/2} \sqrt{2P\bar{Q}} + z_{\beta} \sqrt{P_1Q_1 + P_2Q_2})^2}{(P_2 - P_1)^2}; n = \frac{n'}{4} \left(1 + \sqrt{1 + \frac{4}{n'(P_2 - P_1)}} \right)^2, \text{ where } \bar{p} = \frac{1}{2}(p_1 + p_2) \text{ and } \bar{q} = 1 - \bar{p}$$

to 18% (intervention). If the usual care group also has a small reduction in delirium to 30%, with 150 per group it will be possible to detect a reduction to 13.5% in the intervention group, a 55% relative reduction. Thus, 150 subjects per intervention group will provide sufficient power to detect the hypothesized difference between groups. Power was also examined using the sample size formula for the log-rank test. Assuming a VIF of 117%, $\alpha=.05$, and $\rho=.60$, given the same scenarios as above, with a sample size of 150 per group and power 80%, the detectable λ (hazard ratio) is 2.9. For the continuous

measure (DI), power calculations are based on an assumed σ (population pooled standard deviation) of 3.12, using data from our previous study. The effect size estimate is: δ (DI group difference) and $d = \delta/\sigma$ (where d is Cohen's d). Adjusting for clustering and reliability, the detectable endpoint difference with

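### C.6's claim of sufficient power covers only part of its own hypothesized range: 80% holds at an intervention rate of about 18% or lower, against about 68% at 20% and about 54% at the unreconciled pilot rate of 22%

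*Combined protocol and SAP*

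**What the plan says.** C.6 (Power and effect size) sets the planning effect for the binary outcome: "we hypothesize observing a clinically meaningful 40-60% relative reduction in new delirium from 35% to between 15% and 20" per cent. It gives its basis as the investigators' previous studies and the known effect of the hospital programme from which the intervention was adapted. On method it says: "Sample size was calculated (Figure 1) with the continuity correction,⁷²⁻⁷³ with assumed reliability (R)=.72". It adds a cluster size of 18, an ICC of .01 (VIF 1.17), α=.05 and ρ=0.60. It then claims 80% power with 150 per group for 35% against 18%, and concludes: "Thus, 150 subjects per intervention group will provide sufficient power to detect the hypothesized difference between groups".

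The one other scenario for this outcome has control at 30% and intervention at 13.5%. No power is given for an intervention rate above 18%.

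B.4 (Preliminary studies) describes the pilot: "In 2013 we implemented the intervention during 149 acute illness episodes at the study site". Its result reads: "Delirium occurred during 22% of acute illnesses and 5% of patients were transferred to the hospital". C.6 does not mention the 22%.

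**The concern.** There are two separate gaps.

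1. **Inside C.6.** The hypothesized difference is a range that ends at 20%, but the power calculation stops at 18%. The sufficiency sentence is worded for the whole range.
2. **Between B.4 and C.6.** The only rate that the documents report under this intervention at this site, 22%, lies just outside the planning range, and C.6 does not say why a lower rate is expected.

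This outcome carries the primary Aim 1 analysis in C.7, and C.9 says that the study matters even if it shows no effect. If power is well below 80% over part of the range that the investigators themselves call clinically meaningful, a non-significant result could be misread as evidence that the intervention does not work.

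**Working it through.** **Inputs.** From C.6: control 35%; intervention 18% (powered) and 15-20% (hypothesized); two-sided α=.05 (Figure 1 uses z for α/2); 150 per group; VIF = 1+(18-1)×.01 = 1.17; R=.72. From B.4: 22% of 149 episodes.

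**Step 1: the plan's own figure.** Figure 1 for 35% vs 18%, difference d=.17, mean proportion .265:

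- n' = (1.96×√.38955 + .8416×√.3751)² / .17² = 104.6
- continuity-corrected n = (104.6/4)×(1+√(1+4/(104.6×.17)))² = 116.1
- × 1.17 = 136 per group; then ÷ .72 = 189 per group

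The stated 150 lies between 136 and 189. C.6 does not say how R and ρ enter, so 150 cannot be reproduced from the listed inputs. Power is therefore shown on three readings of the effective n per group:

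- VIF only: 150/1.17 = 128.2
- VIF and R: 150×.72/1.17 = 92.3
- calibrated: 116.1, the value at which 35% vs 18% has exactly the stated 80%

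**Step 2: power at other intervention rates.** Inverting the continuity correction gives n' = (n − 1/d)²/n. Then power = Φ[(d√n' − 1.96√(2p̄q̄)) / √(p₁q₁+p₂q₂)].

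Calibrated reading, 35% vs 20%:

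- n' = (116.1 − 6.67)²/116.1 = 103.1
- z = (.15×10.155 − 1.96×.6315)/.6225 = 0.46, so power is 68%

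Calibrated reading, 35% vs 22%:

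- n' = (116.1 − 7.69)²/116.1 = 101.2
- z = (.13×10.060 − 1.96×.6384)/.6317 = 0.09, so power is 54%

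| Intervention rate (control 35%) | Relative reduction | VIF only | Calibrated | VIF and R |
|---|---|---|---|---|
| 18% | 49% | 84% | 80% | 69% |
| 20% | 43% | 73% | 68% | 56% |
| 22% | 37% | 58% | 54% | 43% |

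Only the calibrated column agrees with C.6's 80% at 18%. The outer columns show how much depends on the unstated handling of R. Using the planned 153 per arm adds about one percentage point: at 22%, 59% with VIF only and 44% with VIF and R.

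**Step 3: precision of the pilot rate.** B.4 gives only the percentage; 22% of 149 is about 33 episodes. The exact 95% interval for 33/149 is 15.8-29.7%. The standard error is √(.22×.78/149) = 3.4 points, so 20% is 0.6 and 18% is 1.2 standard errors below 22%.

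**Step 4: dependence on the control rate.** At 22%, the calibrated reading reaches 80% power only if control is about 40%. If control is 30%, as in C.6's second scenario, and intervention is 22%, power is 19-26% across the readings.

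**The case against.** The strongest reply is that powering on a target effect, rather than on a pilot point estimate, is legitimate, and that C.6 openly names 18%. Its support is said to come from earlier studies and the hospital programme. Those sources are not reproduced, so nobody can say from the documents that 35% or the reduction is unfounded. All of that stands, and nothing here is a calculation error in C.6. The reply does not rescue the sufficiency sentence, which speaks of the hypothesized difference, a range that runs to 20%. C.9 does concede a limited sample size, but in terms of not being able to address all important outcomes, not this one.

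The pilot is also weak evidence about the trial. B.4 does not give the delirium instrument, the assessor or the frequency of assessment. It does not say that delirium present at onset was excluded, or how episodes were selected. The trial uses weekday CAM for incident delirium (C.5) and deliberately sensitive entry criteria (C.2). B.4 counts episodes and gives no number of patients, so repeat episodes or clustering by unit could widen the interval. These points stand too, and they limit what 22% can show.

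A reader might go further in three ways that the documents do not support:

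- **That the pilot shows 18% to be wrong.** Its interval includes 18-20%.
- **That 35% vs 22% is the effect found in the pilot.** The pilot had no control arm and estimated no effect; the 35% comes from C.6.
- **That the long-term care figure in A.1 caps the control rate.** That figure is a prevalence, whereas C.6's 35% is new delirium at any time during an acute illness.

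**Conclusion.** The point holds in limited form. C.6's sufficiency statement is true at an intervention rate of about 18% or lower with control at 35%, and not over the rest of its own range. At 20%, power is about 68% (56-73% depending on how R enters), below 80% on every reading. This needs nothing from the pilot.

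Separately, B.4's 22% is a planning value that C.6 neither uses nor explains. Power there is about 54% (43-58%), on the assumption that control is 35%. The pilot does not refute the 15-20% assumption. It does show that a rate slightly above the range is plausible and should have been addressed.

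A reader might also infer that 150 per group is itself miscalculated. The documents do not support that: the figure lies between two readings of the stated inputs and is only not reproducible as written.

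**What to change.** Keep n=306 and revise C.6 as follows:

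1. Limit the sufficiency sentence to intervention rates of about 18% or lower with control at 35%.
2. Add power at 20% and 22% with control at 35%: about 68% and 54% when calibrated to the stated 80%, with the ranges 56-73% and 43-58%. State how R and ρ enter, so that each range can be replaced by one figure.
3. Reconcile the 15-20% assumption with B.4's 22%. Either explain why a lower rate is expected than in the pilot (for instance, differences in ascertainment or case selection, if that is the reason), or extend the range to include 22%. If it is extended, amend the 40-60% as well, because 22% against 35% is a 37% reduction.
4. State that a non-significant result would not exclude a reduction from 35% to 20-22%.

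The cost is protocol wording only. No patients are added, and the design and analysis do not change. The downside is that the stated power becomes less favourable.

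### C.6: the 80% power for 35% vs 18% at 150 per group does not follow from Figure 1 with the listed inputs, 20% is not covered, and the hazard ratio of 2.9 contradicts the same scenarios

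*Combined protocol and SAP*

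**What the plan says.** All of this is in C.6 of the combined protocol and SAP unless noted.

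- Hypothesis: "we hypothesize observing a clinically meaningful 40-60% relative reduction in new delirium from 35% to between 15% and 20" per cent.
- Endpoint: "For the binary variable, new delirium is defined as when delirium occurs any time during the illness period". C.7 analyses it by logistic regression with clustering modelled.
- Inputs listed for the binary calculation: the continuity correction, R=.72, "cluster size (by unit)=18; intraclass correlation (ICC)=.01; and variance inflation factor (VIF)=1+(cluster size-1)*ICC=1.17", alpha .05, and rho ("estimated average correlation of the outcome measures over time") of 0.60. Figure 1 contains no term for R, VIF or rho, and no number of time points is given for the binary outcome.
- Result: "a sample size of 150 per group will provide 80% power to detect a group difference in new delirium from 35% (baseline") to 18%. A second scenario has 30% falling to 13.5%, also with 150 per group.
- Conclusion: "Thus, 150 subjects per intervention group will provide sufficient power to detect the hypothesized difference between groups".
- Log-rank check: "given the same scenarios as above, with a sample size of 150 per group and power 80%, the detectable λ (hazard ratio) is 2.9".
- DI endpoint: "Adjusting for clustering and reliability, the detectable endpoint difference with" 150 per group is 1.29 (Cohen's d 0.41), with a standard deviation of 3.12.
- DI slope: Table 3 gives n of 117, 132 and 146 and detectable slopes of .238, .252 and .266. The text describes these as adjusted for both reliability and clustering.

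**The concern.** The sample size rests on this calculation, and a reader who puts the listed inputs into the printed formula does not get 150. The sufficiency sentence follows a hypothesized range of 15-20%, yet the main scenario's own 80% point is 18%. The log-rank sentence is offered as support, but its detectable effect is larger than either scenario it refers to.

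C.9 says the study is important even if no effect is observed. A null primary result would then be read as coming from a trial with 80% power for the hypothesized effect. If power is well below that at the weak end of the range, that reading is unsafe.

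**Working it through.** **Inputs (C.6).** Two-sided alpha .05 (Figure 1 uses z for alpha/2): z = 1.960. Power 80%: z = 0.842. VIF = 1 + 17 × .01 = 1.17. R = .72. 150 per group.

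**Step 1. Figure 1 for 35% vs 18%.** The mean rate is .265.

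- n' = (1.960 × √(2 × .265 × .735) + 0.842 × √(.35 × .65 + .18 × .82))² / .17² = (1.2233 + 0.5155)² / .0289 = 104.6.
- With the continuity correction, n = 116.1.

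**Step 2. Apply the listed adjustments.**

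- VIF only: 116.1 × 1.17 = 135.8.
- VIF and R: 116.1 × 1.17 / .72 = 188.6.

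Neither is 150.

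**Step 3. Is dividing by R the plan's own convention?** For the DI endpoint, √(2 × 3.12² × (1.960 + 0.842)² × 1.17 / .72 / 150) = 1.287, and 1.287 / 3.12 = .41. This matches the printed 1.29 and 0.41, so C.6 does use VIF/R there.

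**Step 4. Power at 150 per group.** Let m = 150 / adjustment and Δ = the rate difference. Inverting Figure 1 gives n' = (m − 1/Δ)² / m, and z for power = (Δ√n' − 1.960√(2PQ)) / √(P1Q1 + P2Q2), where P is the mean rate and Q = 1 − P. For 35% vs 18%:

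- VIF and R: m = 92.3, n' = 80.9, z = (1.529 − 1.223) / .612 = 0.50, power 69%.
- VIF only: m = 128.2, n' = 116.7, z = (1.837 − 1.223) / .612 = 1.00, power 84%.

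The same steps for the other rates, with a third column explained in step 5:

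| Comparison | VIF and R | VIF only | VIF, R and a factor 0.8 |
|---|---|---|---|
| 35% vs 15% | 85% | 95% | 92% |
| 35% vs 18% | 69% | 84% | 80% |
| 35% vs 20% | 56% | 73% | 67% |
| 30% vs 13.5% | 72% | 87% | 83% |
| Rate with 80% power, from 35% | 16.1% | 18.8% | 17.95% |

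At the planned 153 per arm, VIF and R give 70% at 18% and 57% at 20%; VIF only gives 85% and 74%.

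**Step 5. Can rho explain 150?** Multiplying by (1 + .60)/2 = 0.8 gives 188.6 × 0.8 = 150.9, with 79.7% power at 150. The same factor gives 108.7 × 1.17 / .72 × 0.8 = 141.3 for 30% vs 13.5%, with a detectable rate of 13.95% rather than the printed 13.5%. R alone fits the second scenario (108.7 / .72 = 151.0) but not the first (116.1 / .72 = 161.2). None of these adjustments fits both.

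**Step 6. Log-rank check.** Under proportional hazards and equal follow-up, HR = ln(1 − control rate) / ln(1 − intervention rate).

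- 35% vs 18%: ln .65 / ln .82 = 2.17.
- 30% vs 13.5%: ln .70 / ln .865 = 2.46.
- An HR of 2.9 from 35% means 1 − .65^(1/2.9) = 13.8%, outside 15-20%.

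With VIF only, the effective events are 150 × .53 / 1.17 = 67.9 and 150 × .435 / 1.17 = 55.8. The detectable HR is 1.97 and 2.12 (Schoenfeld) or 2.03 and 2.20 (Freedman). With VIF and R it is 2.23 and 2.42, or 2.34 and 2.59. None reaches 2.9. If 2.9 were the 80% point (27.7 events, Schoenfeld), power would be about 53% at 2.17 and 66% at 2.46.

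**Step 7. Table 3.** Figure 2 with δ = .27, divided by R only, gives n = 116.5, 131.0 and 145.6 and slopes of .238, .252 and .266. These are the printed values. Adding VIF gives n = 136.2, 153.3 and 170.3 and slopes of .257, .273 and .288.

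**The case against.** **The 80% at 18% is not shown to be wrong.** The two readings, 69% and 84%, lie on either side of it. If 35% and 18% are rates as CAM would observe them, misclassification is already in them and dividing by R discounts twice. A simulation with 9 vs 8 units of 18, ICC .01 and one result per patient gave 83.5% at 18%, using a unit-level t-test rather than the planned model. This stands: a reader might infer that the trial is underpowered at 18%, but the documents support that only if R applies to CAM. However, C.6 lists R among the binary inputs, so the 69% reading cannot be dismissed.

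**The source of 150 is unknown.** A reader might infer that C.6 took a two-time-point repeated-measures credit for rho. The documents do not show this. The factor 0.8 is inferred, it misses the second scenario, and it is not unique: it also equals √(1 − .60²), and 1.17 / .72 × 0.8 = 1.30 = 1.17 / 0.9. What can be said is that such a credit would not suit one any-time yes/no result per patient, which leaves no repeated values to average.

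**The sufficiency sentence may refer only to the two scenarios just computed.** Their relative reductions of 49% and 55% lie within the hypothesized 40-60%, and the 80% points are printed. That reading is possible, but the hypothesis as written runs to 20%, and nothing in the sentence limits it.

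**The log-rank check is secondary.** C.7 plans no time-to-event analysis, C.6 gives no log-rank formula, and the implied ratios need proportional hazards. This lowers its weight but does not remove the contradiction.

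**Conclusion.** The concern holds as a should-fix point of statement and arithmetic. Figure 1 with the listed VIF and R gives 189 per group, not 150, and about 69% power at 150 for 35% vs 18%. If R is not meant for CAM, the figures are 136 and about 84%, and the printed 80% is conservative. The text does not settle which.

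The shortfall at 20% does not depend on that choice: power is 56% with VIF and R, 73% with VIF only, and 67% even with the 0.8 factor that returns about 150 for the main scenario. The sufficiency sentence therefore fails for part of the hypothesized range. At 15% power is at least 85% on each of these readings.

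The HR of 2.9 contradicts its own scenarios (2.17 and 2.46), assuming proportional hazards and equal follow-up. Table 3 is adjusted for R only, contrary to its description. The power figures take C.6's ICC of .01 and cluster size of 18 as given.

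**What to change.** In C.6:

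1. State how R, VIF and rho enter the binary calculation, with no repeated-measures credit for the any-time outcome.
2. Restate power at 150 per group. If R applies to CAM: about 69% for 35% vs 18%, 56% at 20%, 85% at 15% and 72% for 30% vs 13.5%, with 80% reached at about 16%. If it does not, delete R from the binary inputs and state 84%, 73%, 95% and 87%, with 80% reached at about 18.8%.
3. Limit the sufficiency sentence to the part of 15-20% that is covered: 15% to about 16% with R, or 15% to about 18.8% without.
4. Delete the HR 2.9 sentence, or recompute it with a named formula and stated assumptions. With VIF only it would be about 2.0 for 35% vs 18% and 2.1-2.2 for 30% vs 13.5%.
5. In Table 3 and its text, either add the VIF (n about 136, 153 and 170; slopes .257, .273 and .288) or remove the claim of a clustering adjustment.

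The cost is protocol wording only: no added patients and no change to analysis or conduct. The downside is that some stated figures become less favourable.
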